# 6.3 Research Design and Duration

This study will employ a randomized controlled trial (RCT) design. This is a phase III study to determine the effectiveness of a more targeted treatment therapy for VIN II/III (comparing ultrasonic aspiration versus CO2 laser ablation). Potential participants will be identified through the gynecological clinical practices following diagnosis of VIN II/III and will be randomized (1:1) to one of the treatment therapies. Randomization will be stratified for multi-focal disease and HPV status.

Participants will be followed for 1 year following initial treatment for recurrence of vulva dysplasia. Study events will be documented on the study clinical research forms for each visit. The study will continue until 150 participants have completed procedures, which is expected to take approximately 3 years.

# 7. Treatments

Both the Sonopet Ultrasonic Aspirator and the CO2 laser ablation devices are FDA approved devices for the treatment of vulvar dysplasia.

# 7.1 Treatment Assignment

Participants will be randomized 1:1 to either treatment with Ultrasonic Aspiration or CO2 laser ablation after consent of study. Prior to treatment, participants will receive a local anesthesia (lidocaine) to numb the affected area.

- Ultrasonic Aspiration: The Sonopet Ultrasonic Aspirator (manufactured by the Sponsor of this study) provides precise control of soft tissue while simultaneously allowing fine bone dissection in close proximity to delicate structures. The Sonopet Ultrasonic Aspirator is precise in its technique and allows users to independently control power, suction, and irrigation with one hand piece to maximize user control and efficiency. [1] The standard use of the Sonopet aspirator is to obtain a power density of 1,000 watts/cm2 in order to desiccate the tissue. The tissue will change color to a yellow color indicating the epidermal layer had been ablated.
- CO2 Laser Ablation: Lasers provide an efficient method of achieving rapid

excision, coagulation, or vaporization of pelvic abnormalities. The carbon dioxide laser has been considered an effective modality for multiple tasks related to the treatment of intraepithelial neoplasia of the lower genital tract, most commonly for large lesions and for multifocal manifestations of human papilloma virus (HPV). The use of this technology is limited in some areas because of healthcare provider training and experience and because of a lack of availability of equipment. CO2 laser also leaves destruction of the skin at treatment site, and therefore no tissue remains for further histology. However it still remains a preferred treatment modality for VIN among women. [1] The treatment area will be identified by a 3-4 mm region beyond the affected area of the cervix. The entire circumference of the anticipated ablation area is outlined as if outlining a circle with dots. These dots are then connected, and the entire area is ablated with a consistent continuous movement of the laser beam at a pulse of 10 W. The area is measured periodically with a graduated probe used through the colposcope, and the ablation continues to a depth of 7-10 mm

Following treatment participants will be prescribed NSAIDs for pain relief and a topical salve will be placed on the affected area to reduce the risk of scarring. Participants will be asked to refrain from exercise and sexual intercourse for two weeks following treatment.

All study treatment will be conducted by study-trained investigators only. The investigators chosen to participate in the study will all be board-certified gynecologists and will not include providers in-training. Gynecologists are trained to perform vulva sparing treatment in the clinical setting. All investigators elected for this study have a minimum of 3 years of clinical practice following fellowship. The coordinating site will host an in-service for all participating investigators prior to initiation of the study. The in-service will review the standard operating protocols of both devices. Ongoing monitoring and site visits by the PI will also be conducted to insure investigator compliance. In addition, secondary analysis will examine treatment differences per investigator.

Block randomization will be conducted using randomization statistical software. Research personnel will login into the study database and enter information for block randomization on the day of surgery. The randomization software associated with the REDCap data tool will provide the research team with the treatment assignment. Stratification variables will include multifocal disease and HPV status. The statistician responsible for statistical analysis will be blinded to the treatment received.

#### 8. Study Procedures

Participants will conduct the following study visits over 12 months. All costs associated with routine standard of care procedures for diagnosing and treating vulva dysplasia will be the responsibility of the patient and/or their insurance provider.

V0: Screening: All screening will be conducted during routine standard of care (SOC) visits to our gynecologic oncology clinic or colposcopy clinic after review of colposcopy results. Baseline assessment and quality of life assessments will be conducted at this visit, and informed consent will be obtained prior to any study procedures being conducted.

V1: Enrollment Visit: All enrollments will be conducted at the time of treatment visit. Prescribed treatment will be covered by insurance, per SOC.

V2. Pain will be assed at 7-10 days following treatment. Participants will selfevaluate pain by responding to a <5-minute survey (administered electronically or via phone) asking them to rate their pain using a standard patient pain scale.

V3.

Visit 3: Approximately 4-6 weeks following treatment you will be asked to come in for a follow-up visit. A study doctor will assess your scarring at this visit. This is part of routine care. This visit is expected to take approximately 20 minutes.

V4: A SOC 6 month (± 30 days) follow-up will be conducted following treatment. Assessments include physical exam with colposcopy (biopsies performed at the provider's discretion). Assessments at 6 months are to be conducted per standard of care. This visit will take approximately 30 minutes. Quality of life assessments will be conducted at this time. This visit can take place at Colorado, Oklahoma, or Nebraska site, depending on where subject was screened.

V5: End of Treatment: A SOC 12 month ( $\pm$  30 days) follow-up will be conducted following treatment. Assessments include physical exam with colposcopy (biopsies performed at the provider's discretion). Assessments at 12 months are per standard of care. This visit will take approximately 30 minutes. Quality of life assessments will be conducted at this time. This visit can take place at Colorado, Oklahoma, or Nebraska site, depending on where subject was screened.

Study Calendar

Surveys	Pain Assessment	Scar Assessment	Vitals (inc. height/weight)	Physical Exam	(biopsy if needed)	assessment/colposcopy	Adverse Events	Procedures	Medications and	Concomitant	Medical History	Randomization	criteria)	(Inclusion/Exclusion	Confirm eligibility	Informed Consent	Procedures		
×			×	×	×		×	×			×		×			×		Baseline visit	V0: Screening
			×		×		×	×				×						0-30 days following V0	V1: Enrollment
	×																	7-10 days after treatment (survey only)	V2: Pain Assessment
	×	×	×		×		×	×										4-6 weeks after treatment	V3: Scarring Assessment
×	×		×	×	×		×	×										6 months following treatment	V4: 6 month follow up (±30 days)
×	×		×	×	×		×	×										12 months following treatment	V5: 12 month follow up (±30 days)
Ultr CON	× asoi IIRI	nic A 8 # 1	× Aspira 6-070	× tion 1	× vs.	C02	× Lase	× r A	bla	tio	n Vo	ersio	on	04,	/12	/20			Unanticipated Visit

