- Presence of scarring (~30% of women receiving CO2 laser, less than 5% in women receiving ultrasonic aspirator)
- Dysureia or burning (~25% of women)
- Adhesions (less than 5%)
- Infection: yeast, UTI, or other (~10% of women)
- Abnormal discharge (less than 10% of women)
- Eschar (~10% of women). [1]

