#### 11.3.1.1 Anticipated Risks

While the study anticipates minimal risks, the following outlines any potential minimum risk to subjects:

i. Breach of Confidentiality: Data obtained using information from medical records, poses minimum risk. All procedures in which information is being obtained will be conducted per standard of care. There is a risk that a patient's privacy may not be protected. This risk is uncommon.

ii. Discomforts: Persons receiving treatment for Vulvar Intraepithelial Neoplasia can anticipate the following risks: infection, dysuria, burning, adhesions, light bleeding, and discharge. Participants could expect to experience pain and discomfort following surgery for approximately 1 week. Participants should refrain from exercise and sexual intercourse in the two weeks following surgery in order to avoid addition discomfort.

iii. Recurrence: Current treatment for vulva-sparing has a recurrence rate of 25-50% of return disease. Recurrence, left unmanaged, could lead to cancer of the vulva, vagina, or the cervix.

Participation in this study will not have any influence on the patient's current treatment. The study may include risks that are unknown at this time.

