## 14. Statistical Analysis

A per protocol analysis will be conducted. Participants receiving treatment per protocol will be included in the final analysis. Investigators will not have the option to change treatment assignment.

Descriptive statistics using means, frequencies, and percentages will be computed to describe the study population. Participant data will be analyzed employing the per protocol approach. Student's *t*-test (for continuous variables) and chi-square tests (for categorical variables) will be used to compare the two groups for demographic, and secondary outcome variables: pain, scarring, QOL scores. For the primary outcome measure rate of recurrence for each of the study endpoints, 3 months, 6 months and 12 months will be calculated per treatment arm and compared with initial bivariate analysis using chi-square analysis. Additional predictors for recurrence (pain, scarring, sexual function, and general wellness) will be compared similarly with chi-square for categorical variables and t-tests for continuous variables. Potential covariates (age, race, previous disease, etc.) will also be analyzed using bi-variate analysis. Variables found to be significant in the bivariate analysis will be included in multivariable analysis using logistic regression. Logistic regression models will be used to identify significant independent predictors associated with recurrence for each treatment arm. The logistic model will allow for control of study covariates. A p-value of <0.05 will be used to demonstrate statistical significance. IBM SPSS version 22 will be used for all statistical analyses.

Incidence of AEs and SAEs will be compared between treatment arms using chisquare analysis. A p-value of <0.05 will be used to demonstrate statistical significance.

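### No scheduled contact asks about adverse events between treatment and 4-6 weeks, although every woman is already surveyed at day 7-10

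*Combined protocol and SAP*

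**What the plan says.** The Study Calendar in section 8 marks Adverse Events at V0, V1, V3, V4, V5 and in the row labelled "Unanticipated Visit". The V2 row, headed "7-10 days after treatment (survey only)", has a single mark, for Pain Assessment. The visit text in section 8 agrees: "Participants will selfevaluate pain by responding to a <5-minute survey (administered electronically or via phone)". A pain rating is the only content it describes for that contact. The next scheduled contact is V3, "4-6 weeks after treatment".

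Three other sections bear on this:

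- **Collection.** Section 11.3.1 has non-serious adverse events collected from the start of study treatment. Section 11.2.1 has serious events collected from consent.
- **Anticipated events.** Section 11.1 includes "Dysureia or burning (~25% of women)", infection in about 10%, and abnormal discharge in fewer than 10%. Section 11.3.1.1 adds light bleeding. On timing it says: "Participants could expect to experience pain and discomfort following surgery for approximately 1 week".
- **Analysis.** Section 14 states: "Incidence of AEs and SAEs will be compared between treatment arms using chisquare analysis", at p<0.05.

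**The concern.** The rule in section 11.3.1 and the calendar do not meet. Collection formally runs from treatment, but no scheduled step asks about non-serious events until day 28 at the earliest. A woman who has several days of burning, or a minor infection that clears, completes a study survey on day 7-10 and is not asked about it. The concomitant medications and procedures column is also unmarked at V2, so treatment for such an event is not asked about then either.

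Short-lived events are the ones most easily forgotten or left unreported weeks later. If they are under-counted equally in both arms, the section 14 comparison understates incidence and loses power. If they are under-counted unequally, the comparison could be biased in either direction. Section 7.1 states blinding only for the statistician and says nothing of participant blinding, so unequal reporting cannot be ruled out.

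**Working it through.** The plan gives no figure for adverse event capture, so there is nothing of its own to reproduce. The check is a reading of the calendar, followed by arithmetic for scale.

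**1. Calendar by column (section 8)**

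| Contact | Timing | Adverse Events marked | Pain marked |
|---|---|---|---|
| V1 | treatment | yes | no |
| V2 | day 7-10 | no | yes (only mark) |
| V3 | 4-6 weeks | yes | yes |
| Unanticipated visit | unscheduled | yes | yes |

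The table text is broken in extraction, but the V2 row has a single mark and the visit text says the same thing, so misalignment is unlikely.

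**2. Length of the gap**

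- Treatment to V3: 4 × 7 = 28 to 6 × 7 = 42 days.
- V2 to V3: 28 − 10 = 18 to 42 − 7 = 35 days.

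**3. Which events the gap affects**

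| Anticipated event | Scheduled capture before or at V3 | Affected? |
|---|---|---|
| Pain | rated at V2 | no |
| Scarring | visual exam at V3 | no |
| Serious events | collected from consent (11.2.1) | no |
| Dysuria or burning, discharge, minor infection, light bleeding | general adverse event question at V3 only | yes |

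**4. Expected counts at the stated rates, 150 women**

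- Dysuria or burning: 150 × 0.25 = 37.5, about 38.
- Infection: 150 × 0.10 = 15.
- Discharge: fewer than 150 × 0.10 = 15.
- Light bleeding: no rate given.

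**5. Effect on an observed rate**

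Observed rate = true rate × capture fraction. The capture fraction is not in the documents; 50-70% is assumed.

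- 0.25 × 0.50 = 12.5%
- 0.25 × 0.70 = 17.5%

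**6. Illustration of the effect on the test**

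The 10% comparator rate and all capture fractions here are assumptions. Power = Φ[(d − 1.96 × SE₀)/SE₁], where d is the difference in observed rates, SE₀ = √(p̄(1−p̄) × 2/n) and SE₁ = √((p₁(1−p₁) + p₂(1−p₂))/n), two-sided 0.05.

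For 25% v 10% and n = 75 with full capture: p̄ = 0.175, SE₀ = 0.0620, SE₁ = 0.0608. Power = Φ[(0.15 − 0.1216)/0.0608] = Φ(0.467) = 68%.

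| Capture, equal in both arms | Observed rates | n = 75 per arm | n = 62 per arm |
|---|---|---|---|
| 100% | 25% v 10% | 68% | 60% |
| 70% | 17.5% v 7% | 50% | 43% |
| 50% | 12.5% v 5% | 37% | 31% |

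With no true difference (25% in both arms) but capture of 90% v 60%, the observed rates would be 22.5% v 15%. The chance of p<0.05 in that direction would then be about 22% (n = 75) or 19% (n = 62).

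**The case against.** The strongest reply is that the plan is not silent on early events. Unanticipated visits carry an adverse event mark, and serious events are collected from consent. Pain, the first anticipated event listed in section 11.1, is rated at V2. Scarring, the only event given different rates by arm, is found by examination. Concomitant medications and procedures are recorded at V3, and section 4 has clinical data verified against medical records, so a treated infection has a source other than memory. All of this stands. It confines the point to transient, non-serious events, mainly those that did not lead to care.

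Second, section 11.3.1.1 gives a duration only for pain and discomfort. The early timing of the other events is inferred from their listing in the same paragraph, and an event starting after day 10 would be missed by a V2 question too. That also stands.

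Third, section 11.1 describes the two devices' risks as similar apart from scarring, so a 25% v 10% contrast is not one the protocol expects. Even with full capture, its power would be only 60-68%. The power figures are therefore illustration, not evidence of a loss in this trial.

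Fourth, adverse event incidence is neither a hypothesis in section 2.1 nor a listed secondary outcome. This limits the importance of the point but does not remove it, because section 14 still plans a formal comparison.

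Finally, if a woman knows her device at V3 she also knows it at V2. Earlier questioning shortens recall but does not cure reporting bias.

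**Conclusion.** The point holds within limits. No adverse event elicitation is scheduled between treatment and 4-6 weeks, while non-serious collection starts at treatment, incidence is tested by arm, and an existing day 7-10 survey could carry the questions. Dysuria or burning, discharge, minor infection and light bleeding are left to recall at V3 or to unprompted presentation. The size of the effect is unknown; the 12.5-17.5% range rests entirely on the assumed 50-70% capture.

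A reader might infer three stronger things that the documents do not support:

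- **That early events cannot reach the site at all.** Unanticipated visits and the serious event rules provide routes.
- **That the whole adverse event comparison rests on recall.** Pain and scarring have dedicated assessments.
- **That recall will differ by arm or that power will be lost by a known amount.** Participant blinding is not stated, so differential recall is possible. It is not shown, and the inputs needed to size it are absent.

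This is an inexpensive improvement to a planned safety comparison. It does not affect the primary analysis or the listed secondary analyses.

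**What to change.** Mark Adverse Events at V2 in the Study Calendar. Add a few fixed yes/no items to the existing electronic or phone survey, worded identically in both arms, for the events in sections 11.1 and 11.3.1.1 that a woman can report herself: burning or dysuria, discharge, infection or treatment for it, and light bleeding. Have existing site staff follow up each positive answer and enter it in the adverse event log with its onset date. At V3, ask about events since V2, or since treatment if V2 was missed. Eschar is not readily self-reported, so these items would not capture it.

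The cost is about one more minute in a survey of under five minutes, some follow-up calls, and a form and IRB amendment. No new visit or procedure is needed. Adverse event counts will be somewhat higher in both arms, and reporting bias from knowing the device will remain.

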## 9. Study Assessments

Investigators will be expected to use the treatment assignment provided and will not have the option to elect a preferred treatment. Data will be analyzed per protocol so only participants receiving the correct treatment assignment will be included in the final analysis. Training of all study investigators will be conducted prior to initiation and regular monitoring and site visits will be conducted throughout the study to ensure continued compliance. Secondary analysis will look at differences in treatment performance and scarring assessment among the investigators. Any differences will be noted in any publication of the data.

Women with gynecologic disease are afflicted with a number of psychological and social issues disrupting quality of life. Patients report changes to their social and functional well-being as well as changes to their sexual health. Quality of life assessments will be conducted at baseline, 6, and 12-month follow-ups. Patients struggling with psychosocial aspects will be referred for clinical consult as needed. The University of Colorado Hospital staffs a group of social workers who are available to meet with patients in a private clinical office if the patient expresses a psychosocial issue that requires attention.

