# 2.1 Hypothesis

- Hypothesis 1: Treatment for VIN II/III with ultrasonic aspiration will have a 60% reduction in recurrence rates over 12 months as compared to CO2 laser aspiration.
- Hypothesis 2: Treatment for VIN II/III with ultrasonic aspiration will demonstrate decreased incidence of pain and scarring up to 6 weeks following treatment as compared to CO2 laser aspiration.

Hypothesis 3: Treatment for VIN II/III with ultrasonic aspiration will demonstrate a decrease in change of sexual and psychosocial function (as demonstrated with validated instruments) in the 12 months following treatment as compared to CO2 laser aspiration.

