## 6.2 Sample Size

Based on previous studies, approximately 37.5% of patients will reoccur within 12 months with traditional treatment (CO2 laser). [5, 7-13] We can detect a 60% reduction of recurrence to a rate of 15% at 80% power and an alpha of 0.05 with 62 patients per arm. [3] We will enroll an additional 13 patients per arm (n=75 per arm, 150 total) to account for noncompliance, lost to follow-up or misclassification diagnosis.

Approximately 75% of participants will be recruited at the coordinating site, University of Colorado Denver. The other 25% of participants will be recruited at the secondary sites Regional West Medical Center, and The University of Oklahoma are the secondary sites recruiting participants.

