# 15.1.1 Protocol Amendments

Any amendments to the protocol will be first reviewed by the study team and then submitted to the IRB of the lead site for approval. Sub-sites will then be required to submit the protocol amendment to their local IRB and maintain all submission and approvals in their regulatory files. Sites will not initiate any changes to study procedures until after approval of the protocol amendment by their local IRB. Insignificant changes (i.e. personnel changes) may not have to be submitted to the sponsor and/or lead site first.

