# 15.1.2 Subject Withdrawals

All participant documentation up until study withdrawal will be maintained and used for data analysis. In the event a participant is lost to follow-up, 3 documented attempts will be made to contact the participant to conduct an end of treatment visit. If after 3 attempts, the participant still does not return, a certified letter noting withdraw from study should be sent to the participant. The study coordinator will maintain a return receipt for such. Additionally, the study coordinator should send a self-addressed package to the participant for return of any study medications and/or study documents.

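### The only planned analysis of recurrence is per protocol, so a superiority claim would rest on a comparison that randomization does not fully protect

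*Combined protocol and SAP*

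**What the plan says.** Section 9 (Study Assessments) defines the analysis set by the treatment received: "Data will be analyzed per protocol so only participants receiving the correct treatment assignment will be included in the final analysis". Section 14 (Statistical Analysis) opens with "A per protocol analysis will be conducted. Participants receiving treatment per protocol will be included in the final analysis" and repeats it: "Participant data will be analyzed employing the per protocol approach". Neither section, nor any other, plans an intention-to-treat, modified intention-to-treat or other as-randomized analysis.

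Hypothesis 1 in section 2.1 is directional: "ultrasonic aspiration will have a 60% reduction in recurrence rates over 12 months", relative to laser. Section 6.2 powers the trial for a difference, 37.5% against 15%, and gives no non-inferiority margin.

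Three other places bear on the point:

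- Section 7.1 places allocation close to treatment: "Research personnel will login into the study database and enter information for block randomization on the day of surgery". Sections 9 and 14 give investigators no choice of device.
- Section 6.2 adds 13 women per arm "to account for noncompliance, lost to follow-up or misclassification diagnosis", without a rate for any one cause.
- Section 15.1.2 says of withdrawals: "All participant documentation up until study withdrawal will be maintained and used for data analysis".

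**The concern.** Randomization makes the arms comparable when they are formed. Whether a woman then receives her assigned device is settled afterwards. Removing those who did not receive it leaves two groups that need not be comparable. For a superiority question the usual primary analysis is therefore by assigned arm. The usual reason for giving per protocol prominence, a non-inferiority margin, is absent here.

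The documents suggest how exclusion could be related both to prognosis and to arm, although this is an inference. Section 7.1 describes the laser as most often used for large or multifocal disease, and section 1.1 says recurrence is more frequent with multifocal disease. A woman with extensive disease assigned to aspiration but treated by laser would leave the aspiration arm and make aspiration look better. Section 7.1 also says that training and equipment limit laser use, which could remove women from the laser arm. Stratifying on multifocal disease and HPV status balances the arms at randomization, not after exclusions.

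Section 15.1.2 does not repair this. Keeping data up to withdrawal does not bring back women excluded for receiving the wrong device, and it does not say how a missing 12-month status is handled. If bias arose, no planned analysis would show the outcomes of the excluded women.

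**Working it through.** **Inputs from section 6.2.** Laser recurrence 37.5%, aspiration 15%, alpha 0.05, power 80%, 62 per arm plus 13, giving 75. Sidedness is not stated, so I assume two-sided.

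**The plan's own figure.** The pooled two-proportion formula without continuity correction is

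n = [1.96·√(2·0.2625·0.7375) + 0.8416·√(0.375·0.625 + 0.15·0.85)]² / 0.225² = 58.8, so 59 per arm.

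The stated 62 is slightly conservative (82.1% power by the same method), and 62 + 13 = 75 is consistent. Nothing below depends on the gap between 59 and 62.

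**Assumptions.** The documents give no rates of non-receipt or crossover, and no recurrence risk in excluded women. I take k = 2, 4 or 8 of 75 excluded from each arm. Exclusion is outcome-related in one arm only, and the excluded women in that arm recur at r = 60% to 100%. Rejection probabilities come from full binomial enumeration of the uncorrected two-sided chi-square test with 75 − k per arm.

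The per-protocol rate in the selected arm, when its true rate is 37.5%, is

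(75·0.375 − k·r) / (75 − k) = (28.125 − k·r) / (75 − k).

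For k = 4: r = 0.60 gives 25.725/71 = 36.2%, and r = 1.00 gives 24.125/71 = 34.0%. The spurious benefit is 1.3 to 3.5 points.

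**(a) No true difference, selection in the aspiration arm only**

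| Excluded per arm | Spurious benefit (points) | Two-sided type I error | False claim for aspiration (nominal 2.5%) |
|---|---|---|---|
| 2 | 0.6 to 1.7 | 5.1% to 5.5% | 3.0% to 4.0% |
| 4 | 1.3 to 3.5 | 5.2% to 7.2% | 3.5% to 6.4% |
| 8 | 2.7 to 7.5 | 6.2% to 15.2% | 5.1% to 15.0% |

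Selection in the laser arm only gives the same totals, in favour of laser.

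**(b) Same selection in both arms, no true difference.** Type I error is 5.0% to 5.1% for every k.

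**(c) True 37.5% against 15%, selection in the laser arm only.** The reference is unrelated exclusion of the same number.

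| Excluded per arm | Power, unrelated exclusion | Power, selected exclusion |
|---|---|---|
| 2 | 88% | 83% to 87% |
| 4 | 88% | 77% to 84% |
| 8 | 86% | 56% to 77% |

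**What the as-randomized analysis costs in power.** Let a fraction c receive the other device. The aspiration-arm rate becomes (1 − c)·15% + c·37.5%. The laser-arm rate stays at 37.5% if crossover is only from aspiration to laser (one-way), or becomes (1 − c)·37.5% + c·15% if it occurs in both arms (two-way). At c = 5% these are 16.1% and 36.4%, so the 22.5-point difference becomes 21.4 points one-way or 20.3 two-way.

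| Crossover | Power with 75 per arm observed, one-way | Two-way |
|---|---|---|
| 0% | 89% | 89% |
| 5% | 85% | 82% |
| 10% | 80% | 72% |

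At 5% crossover, 80% power needs about 65 (one-way) or 71 (two-way) women observed per arm. At 2% it needs 62 (80.8%, one-way) or 63 (80.2%, two-way).

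**The case against.** The strongest reply is that the design leaves little room for this bias. Allocation is made on the day of surgery, treatment is a procedure at that visit, and investigators cannot choose the device. The set is defined only by receipt of the correct treatment, so exclusion is settled before recurrence is known. The figures that matter need one-arm selection and excluded women recurring well above 37.5%. The 15.2% needs 8 excluded per arm, with every excluded aspiration woman recurring and the laser exclusions unrelated to outcome. The 13-per-arm allowance pools three causes and cannot support 8 wrong-device exclusions.

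This stands as a limit on size. Two to four exclusions is the more natural range to read, and at two the effect is slight. It does not supply the missing analysis: exclusion settled before recurrence can still depend on disease extent, which predicts recurrence.

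A second reply is that baseline comparisons (section 14) and the deviation listing in the annual safety report (section 13.2) could reveal a problem. They could show imbalance in measured factors or the number of deviations, but not the outcomes of excluded women.

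A third is that dilution could be costly. At 10% crossover with only 62 per arm observed, as-randomized power is about 73% (one-way) or 63% (two-way). That is correct and should be stated openly. But if non-receipt is as rare as the first reply supposes, the dilution is small too.

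**Conclusion.** The concern holds. The text is clear: per protocol is the only analysis set for the primary endpoint of a trial with a superiority hypothesis. This needs correcting because the primary comparison has no as-randomized version, not because a bias of a given size has been shown. With 2 to 4 exclusions per arm and one-sided selection, the type I error is 5.1% to 7.2%. With 8 it could reach 15.2%, and the reverse pattern could cut power from 86% to as low as 56%. All of these rest on assumed exclusion numbers and recurrence risks. If exclusions are few, unrelated to prognosis, or alike in both arms, the bias is small or nil. The change matters before results are seen: outcomes not collected in excluded women may be unrecoverable, and an as-randomized analysis chosen afterwards would carry little weight.

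**What to change.** Core changes to sections 9 and 14:

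1. Make the primary recurrence analysis all randomized women in their assigned arm, whichever device was used.
2. Keep per protocol as a labelled sensitivity analysis, and report exclusions by arm with reasons.
3. Record recurrence status to 12 months, from standard-of-care follow-up, in women who did not receive the assigned device and in those discontinued for reasons other than recurrence, such as the serious adverse events of section 11.2. Women discontinued at recurrence already have their primary outcome.

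Useful additions, which the core changes do not depend on: a sensitivity analysis that varies the assumed recurrence rate by arm in women with missing status; one rule for both arms, based on pre-randomization pathology, for women later found not to have VIN II/III; and, in section 6.2, the crossover and loss rates assumed within the existing 13 per arm, with the resulting power.

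The cost is a protocol amendment approved by the lead-site IRB and then locally (section 15.1.1: "Sub-sites will then be required to submit the protocol amendment to their local IRB"), possibly a consent revision for outcome capture after discontinuation, and one data-capture line. The statistical downside is dilution if there is crossover. No extra patients are proposed.
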